#### **Phase 2 study**

We will accrue a maximum of 24 patients at a rate of 2 patient per month. The primary outcome for this trial is overall response rate.

#### **8.2 Dose escalation scheme for phase I**

Cohorts of 3-6 patients each will be treated with increasing doses of ruxolitinib in a progression of 10mg, 15mg, 25 mg and 50 mg twice daily.

At least 3 patients will be treated at each dose level. All patients treated at the preceding dose level will be observed a minimum of 5 weeks before dose escalation occurs. Dose escalation will proceed as follows:

- If none of the initial 3 evaluable patients in a cohort experiences first cycle dose limiting toxicity (DLT), then a new cohort of 3 patients will be treated at the next higher dose level.
- If one of 3 evaluable patients in a cohort experiences DLT, then up to an additional 3 patients will be treated at the same dose level. Escalation will continue if only one of the 6 patients experiences a DLT.
- In the event that 2 of 3 evaluable patients, or 2 of 6 patients in the first cohort experiences a DLT, then the next cohort of patients will be treated at a lower dose level (dose level -1) and no further dose escalation will occur in this step. Three patients will be enrolled at this dose level, if 0 or 1 patients experiences a DLT, a further 3 patients will be enrolled at this dose level. If overall 0 or 1 patient experiences a DLT at this dose level, this dose will be established as the maximum tolerated dose (MTD).
- If two or more evaluable patients in the cohort experience DLT, then the maximum tolerated dose (MTD) will have been exceeded, and no further dose escalation will occur. The previous dose will be considered as the MTD.
- If only three patients were treated at the dose level under consideration as the MTD, then up to an additional 3 patients will be accrued. If no more than one patient at that dose level experiences DLT, then that dose level will be confirmed as the MTD. If two or more patients in that cohort experience DLT, then the previous dose level will be studied in the same fashion.

### **8.3 Definition of DLT and MTD:**

For the purposes of assessing safety, DLTs will be defined as those adverse events occurring in the first cycle (i.e. 28 days) of therapy that are not clearly related to disease, intercurrent illness or concurrent medication. These events will be defined based on the NCI CTCAE version 4 as follows:

- Any Grade 3 or higher non-hematologic toxicity (with the exceptions of Grade 3 or higher nausea, vomiting, or diarrhea, which will be considered DLTs only after optimal prophylactic measures have been prescribed; Grade 3 elevations of AST/ALT must be sustained for more than 4 days or reach Grade 4 to be considered a DLT. Grade 3 elevations in bilirubin must occur in the setting of a direct bilirubin  $>1$  to be considered a DLT. Fatigue must be Grade 4 to be considered a DLT)
- Any Grade 4 hematologic toxicity lasting at least 42 days from the first day of the last cycle of therapy with a bone marrow cellularity of  $\leq 5\%$  and no evidence of leukemia. No dose modification will occur until any potential DLTs is fully assessed

MTD is defined as the highest dose studied for which the incidence of DLT is less than 17% (1 out of 6).

**Table 2 - Criteria for dose modifications of RUXOLITINIB due to study drug-related toxicity – These must be clearly related to ruxolitinib and not the underlying disease; to be determined by PI and treating physician**

Worst Toxicity CTCAE Grade* unless otherwise specified (Value)	Dose Modification Guidelines At any time during a cycle of therapy (including intended day of dosing)	
HEMATOLOGICAL TOXICITIES		
Thrombocytopenia	< 20 x 10  /L	Interrupt study treatment dosing until resolved to ≥ 20 x 10  /L, then restart study treatment at reduced level as per Table 5
	> 20 x 10  /L + grade 3 bleed	Interrupt study treatment dosing until bleeding is resolved and platelet count is at level before bleed was noted, then resume study treatment at reduced level as per Table 5
Neutropenia (ANC)	Grade 4 (ANC < 0.5 x 10  /L)	Interrupt study treatment dosing until resolved to ≤ grade 2, or baseline, then: 
 
• If resolved within 7 days restart study treatment at an unchanged dose level
 
• If resolved in more than 7 days then restart study treatment at reduced level as per Table 5
 

	Febrile neutropenia (ANC < 1.0 x 10  /L, fever ≥ 38.5°C)	Interrupt study treatment dosing until fever resolved and ANC ≤ grade 2, then restart study treatment at reduced level as per Table 5

Worst Toxicity CTCAE Grade* unless otherwise specified (Value)		Dose Modification Guidelines At any time during a cycle of therapy (including intended day of dosing)
Anemia# only requires dose reductions after cycle 6	Doubling of transfusion frequency from baseline or hemoglobin	Hold Ruxolitinib only and continue Decitabine, if hemoglobin (or transfusion frequency) returns to baseline within 28 days restart Ruxolitinib at same dose, if this recurs again then reduce dose as per Table 5
NON-HEMATOLOGICAL TOXICITIES		
GASTROINTESTINAL		
Diarrhea	Grade 2 (4-6 stools/day over baseline, etc) despite the use of optimal antidiarrheal medications	Hold Ruxolitinib dosing until resolved to $\leq$ grade 1, or baseline, then restart at unchanged dose level
	Grade 3 ( $\geq$ 7 stools/day over baseline, etc) despite the use of optimal antidiarrheal medications	Hold Ruxolitinib dosing until resolved to $\leq$ grade 1, or baseline, then restart study treatment at reduced level as per Table 5
	Grade 4 (life-threatening consequences, hemodynamic collapse, etc) despite the use of optimal antidiarrheal medications	Permanently discontinue study treatment dosing
Vomiting/Nausea***	Grade 1 & 2 not requiring treatment or controlled using standard anti-emetics	Maintain dose level
	Grade 3 or 4 vomiting or Grade 3 nausea that cannot be controlled despite the use of standard anti-emetics	Interrupt study treatment dosing until resolved to $\leq$ grade 1, or baseline, then restart study treatment at reduced level as per Table 5
HEPATIC		
Total Bilirubin	Grade 3 or 4	Interrupt study treatment dosing until resolved to $\leq$ grade 2, or baseline, then restart study treatment at reduced level as per Table 5

Worst Toxicity CTCAE Grade* unless otherwise specified (Value)	Dose Modification Guidelines At any time during a cycle of therapy (including intended day of dosing)
Note: If Grade 3 or Grade 4 hyperbilirubinemia is due to the indirect component only, and hemolysis as the etiology has been ruled out as per institutional guidelines (e.g., review of peripheral blood smear and haptoglobin determination), then reduction of one dose level and continuation of treatment is at the discretion of the Investigator.	
AST/SGOT, ALT/SGPT	> 5-10 x ULN
	
Interrupt study treatment dosing until resolved to <math>\leq</math> grade 1 (or <math>\leq</math> grade 2 if liver infiltration with tumor is present), or baseline, then:
 
 
• If resolved within 7 days, then: 
 
• restart study treatment at unchanged dose level
 
 
 
• If resolved in more than 7 days, then restart study treatment at reduced level as per Table 5
 

	> 10 x ULN

All dose modifications should be based on the worst preceding toxicity.
 
* Common Terminology Criteria for Adverse Events (CTCAE Version 4.0)
 
** It is critical that electrolyte abnormalities be followed closely and corrected prior to dosing
 
*** See also concomitant medication section
	

If Ruxolitinib is required to be held based on the dose holding and modification rules above, then it is permissible to use a prednisone taper starting at a dose of 20mg or more a day at the discretion of the investigator to reduce the rebound symptoms that have been well documented in previous studies with Ruxolitinib.

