**Table 1 – RUXOLITINIB dose**

Dose level	RUXOLITINIB (mg PO) (x 28 days)	No of evaluable patients
0	10 BID	3
1	15 BID	3
2	25 BID	3
3	50 BID	3

We will utilize the above design format to determine the tolerable dose of RUXOLITINIB to be used in combination with decitabine, with 25 mg PO BID as the target dose. The enrollment of participants will be staggered; all the participants in each cohort will finish the first cycle of therapy followed by 7 days of observation (i.e. day 35 of therapy) before proceeding to the next cohort. Subsequence cycles will begin on the first day of decitabine therapy and, in the absence of toxicity, RUXOLITINIB administration will not be interrupted. Patients who come off the study during the first cycle for reasons other than development of dose limiting toxicity (e.g. disease progression) will be replaced in order to ensure adequate chance for the assessment of DLT.

If grade 3-4 non-hematological RUXOLITINIB-related toxicities are observed in ≥ 2/6 patients, this dose level would exceed the MTD.

If grade 3-4 RUXOLITINIB-related toxicities are observed in 0-1/6 patients, the study will continue at the RUXOLITINIB dose of 15, 25, and 50 mg P.O. BID x 28 days plus chemotherapy, as outlined above. We will examine the dose of 50 mg BID to assess its tolerability and if well tolerated, this will be the dose to move to phase II. However, the target dose for phase II is 25 mg po BID x 28 days.

Cycles will be repeated approximately every 4 to 6 weeks, depending on the recovery of the blood counts and will continue until clinically significant progression, withdrawal of consent or unacceptable toxicity for a maximum of 24 cycles (see section 13.0).

Toxicities to be monitored include any grade 3 or 4 non-hematological toxicity felt to be related to RUXOLITINIB and prolonged cytopenias (lasting for more than 42 days after the initiation of the treatment) felt to be related to the treatment and not the underlying disease. Patients with prolonged cytopenias should have a bone marrow exam around day 42 to establish whether this is due to the treatment or whether there is persistent disease. In the case of the former, treatment should be discontinued.

Prior to advancing/changing dose levels, a cohort summary must be completed and submitted to the IND Medical Monitor for review.

Each cohort will have up to 6 patients enrolled.

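### The only hematologic DLT needs at least 42 days, but DLTs are confined to a 28-day cycle and the next cohort may open at day 35

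*Combined protocol and SAP*

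**What the plan says.** Sections 3.1 and 8.3 define DLTs in the same words: "DLTs will be defined as those adverse events occurring in the first cycle (i.e. 28 days) of therapy". Section 8.2 escalates on first-cycle DLTs. Section 13.0 (Dose Escalation Procedures) ties the MTD to DLTs in the first cycle and describes a cycle as 5 days of decitabine and 28 days of ruxolitinib, with ruxolitinib allowed to run on until the next cycle starts.

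The definition contains one hematologic DLT: "Any Grade 4 hematologic toxicity lasting at least 42 days from the first day of the last cycle of therapy", with marrow cellularity of 5% or less and no evidence of leukemia. It is followed by the sentence "No dose modification will occur until any potential DLTs is fully assessed".

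On timing, Section 8.1 (text under Table 1) says that all participants in a cohort "will finish the first cycle of therapy followed by 7 days of observation (i.e. day 35 of therapy) before proceeding to the next cohort". Section 8.2 says: "All patients treated at the preceding dose level will be observed a minimum of 5 weeks before dose escalation occurs". For cytopenias, Section 8.1 counts more than 42 days from the start of treatment and adds: "Patients with prolonged cytopenias should have a bone marrow exam around day 42 to establish whether this is due to the treatment". It also requires a report before any change of dose level: "Prior to advancing/changing dose levels, a cohort summary must be completed and submitted to the IND Medical Monitor for review".

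**The concern.** A 3+3 design works only if every event that counts as a DLT can be known for every patient on whom the escalation decision rests. Here three clocks do not fit together: a 28-day window, a 35-day wait and a 42-day criterion.

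The event at issue is a plausible one. Section 10.0 expects myelosuppression from both drugs and calls that of decitabine acceptable in this setting, yet the protocol still lists prolonged aplasia as a DLT. If the stated timing is followed, a higher ruxolitinib dose can open before that DLT can be established in every patient at the dose below. Whether the event counts toward the MTD depends on how the study team reads the definition. Assessment of DLT and MTD is the first endpoint in Section 1.3. The phase II toxicity monitoring in Section 13.0 limits later consequences but plays no part in phase I escalation.

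**Working it through.** **Dates**

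| Element | Section | Day |
|---|---|---|
| DLT window closes | 3.1, 8.3 | 28 |
| Earliest opening of next cohort | 8.1 | 28 + 7 = 35 |
| Minimum observation before escalation | 8.2 | 5 × 7 = 35 |
| Hematologic DLT can first be met | 3.1, 8.3 | 42 |
| Marrow exam to settle the cause | 8.1 | about 42 |

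Sections 8.1 and 8.2 agree with each other at day 35. The hematologic criterion falls 42 − 28 = 14 days after the window and 42 − 35 = 7 days after the earliest escalation, before any time for a marrow result.

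**Two readings of the window**

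1. *The DLT must be complete within 28 days.* An event that needs 42 days never qualifies, so the hematologic DLT has no effect.
2. *Onset within 28 days is enough.* The event qualifies. When the last patient is at day 35, a patient has reached day 42 only by having started at least 7 days earlier. The last patient, and any who started less than 7 days before, are undetermined.

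**The starting day.** Sections 3.1 and 8.3 count from the first day of the last cycle; Section 8.1 counts from the start of treatment. These coincide until cycle 2 begins. Cycles repeat every 4 to 6 weeks and Section 3.2 allows an early start, so the first clock can restart before cycle 1 has been assessed.

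**Illustration of size.** The documents give no DLT rates, so these are assumptions: non-hematologic DLT rate n, prolonged aplasia rate h, independent, so p = 1 − (1 − n)(1 − h). The 3+3 rule escalates on 0 of 3, or on 1 of 3 followed by 0 of the next 3.

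- Aplasia always counted: (1 − p)³ + 3p(1 − p)⁵.
- Aplasia never counted: the same formula with p = n.
- Last patient of each three missed: observed probabilities are p, p, n in each three, and P(escalate) = P(0) + P(1) × P(0).
- As the previous line, but with the first three fully known when the second three are judged.

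Worked case, n = h = 0.10, so p = 1 − 0.9 × 0.9 = 0.19:

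- Counted: 0.81³ + 3 × 0.19 × 0.81⁵ = 0.531 + 0.199 = 0.730.
- Never counted: 0.9³ + 3 × 0.1 × 0.9⁵ = 0.729 + 0.177 = 0.906.
- Last missed: P(0) = 0.81² × 0.9 = 0.590; P(1) = 2 × 0.19 × 0.81 × 0.9 + 0.81² × 0.1 = 0.343; 0.590 + 0.343 × 0.590 = 0.793.
- First three known later: exactly one true and visible DLT in the first three has probability 2 × 0.19 × 0.81² + 0.81² × 0.1 = 0.315; 0.590 + 0.315 × 0.590 = 0.776.

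Chance of escalating past the dose, n = 10%:

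| Aplasia rate | Counted | Last missed | First three known later | Never counted |
|---|---|---|---|---|
| 5% | 82% | 85% | 85% | 91% |
| 10% | 73% | 79% | 78% | 91% |
| 20% | 54% | 66% | 63% | 91% |
| 30% | 36% | 52% | 48% | 91% |

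From unrounded values, partial visibility adds 2 to 3 points at 5% aplasia and 12 to 16 points at 30%. Never counting adds 8 to 55 points. With n = 5% and the same four aplasia rates, the figures are 91/82/62/42% counted, 93/88/75/61% with the last patient missed, and 97% never counted.

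**The case against.** The strongest reply is that an undetermined case is not an unseen one. Table 3 requires blood counts at least weekly in cycle 1 and at least every two weeks afterwards, so a patient heading for 42 days of Grade 4 toxicity would normally be visibly cytopenic at day 35. Two provisions could then hold escalation: "No dose modification will occur until any potential DLTs is fully assessed", and the cohort summary sent to the IND Medical Monitor. If they always do, the shift in escalation probability is zero. This stands as a limit on the size, but it does not cure the conflict. No rule says that a pending case holds escalation, while Section 8.2 directs escalation when none of three patients has had a DLT. The summary carries no day-42 condition.

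The dose-modification sentence can be argued either way. It sits within the hematologic DLT criterion, and a patient-level reading clashes with Table 2, which requires treatment to be interrupted for Grade 4 neutropenia at any time in a cycle. That favors a cohort-level reading. But Section 8.1 and Table 2 use the term for changes within a patient, and a cohort-level reading sits badly with the day-35 opening. It remains ambiguous.

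Other points stand in part:

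- Day 35 is a minimum and enrollment is staggered, so under the onset reading few patients may be affected.
- Cycle 2 depends on count recovery, so the two starting days would ordinarily coincide in a persistently cytopenic patient.
- The largest shift needs both the reading that voids a listed DLT and a 30% aplasia rate, which nothing in the documents supports.
- Declaring an MTD requires six patients with at most one first-cycle DLT. A late-established aplasia could still count there under the onset reading, but that does not undo the earlier exposure of the next cohort.

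**Conclusion.** The concern holds. As written, the listed hematologic DLT either can never count or is not assured to be known for the most recently enrolled patients at the earliest permitted escalation. This follows from the protocol's own day counts and needs no assumption about rates.

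The effect on escalation cannot be determined from the documents. In the illustration with a 10% non-hematologic rate it is small if aplasia is rare (2 to 3 points at 5%) and material if it is common (12 to 16 points at 30%), with 8 to 55 points as the upper bound under the literal reading. These figures assume independence and that a pending case does not stop escalation. They describe passing one dose level, not the final choice of MTD. The matter must be fixed because the phase I decision rule cannot be applied consistently as it stands.

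**What to change.** Reconcile Sections 3.1, 8.1, 8.2, 8.3 and 13.0 so that the following are compatible and every listed DLT can be assessed before the escalation decision:

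- the DLT window, including whether onset within it is sufficient;
- the hematologic criterion, including whether it refers to the first or the last cycle and the day from which the 42 days run;
- the earliest time at which the next cohort may open.

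State whether the sentence on dose modification governs cohort escalation, and what happens to the decision while a potential DLT is pending. Which timing is clinically right is for the sponsor to decide.

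The cost is protocol wording. If the cohort-opening time is the element changed, it adds about one week per cohort (day 42 against day 35), plus any time for the marrow result.

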**3.0 STUDY DESIGN****3.1 Design**

In this non-randomized Phase I/II investigator-initiated, single center trial, cohorts of patients will be treated with increasing doses of ruxolitinib in combination with a decitabine at a dose of 20mg/m^2 daily intravenously over 5 days. We will use an initial dose of ruxolitinib of 10 mg orally twice daily. Patients will receive ruxolitinib for the first 28 days in addition to decitabine on days 1-5 of each cycle. Cycles will be repeated every 4-6 weeks depending on tolerance and the recovery of the counts. Patients who become eligible for allogenic stem cell transplant may leave the study at any time after the first cycle.

After the first cycle of therapy, modifications to the dose of Ruxolitinib felt to be in the best interest of the patient are allowed after discussion with the Principal Investigator of the study and with the documentation of the discussion in the patient's medical records.

For the purposes of assessing safety, DLTs will be defined as those adverse events occurring in the first cycle (i.e. 28 days) of therapy that are not clearly related to disease, intercurrent illness or concurrent medication. These events will be defined based on the NCI CTCAE version 4 as follows:

- Any Grade 3 or higher non-hematologic toxicity (with the exceptions of Grade 3 or higher nausea, vomiting, or diarrhea, which will be considered DLTs only after optimal prophylactic measures have been prescribed; Grade 3 elevations of AST/ALT must be sustained for more than 4 days or reach Grade 4 to be considered a DLT. Grade 3 elevations in bilirubin must occur in the setting of a direct bilirubin >1 to be considered a DLT. Fatigue must be Grade 4 to be considered a DLT)
- Any Grade 4 hematologic toxicity lasting at least 42 days from the first day of the last cycle of therapy with a bone marrow cellularity of ≤5% and no evidence of leukemia. No dose modification will occur until any potential DLTs is fully assessed

MTD is defined as the highest dose studied for which the incidence of DLT is less than or equal to 17% (1 out of 6).

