## **Dose modifications during induction therapy in phase I and II:**

Patients who experience RUXOLITINIB-specific (defined as determined by the principal investigator) grade 3-4 extramedullary toxicities during induction cycle #1, and who are not in CR after cycle #1, may receive a second induction course at the next lower dose with respect to RUXOLITINIB (as defined in table1 on page 14). Other dose modification schedules felt to be in the best interest of the patient may be permitted, after discussion with the principal investigator with the documentation of the discussion in the patient's medical records. There will be no dose modifications of decitabine for either induction cycle #1, or second induction course, secondary to myelosuppression.

Adjustment of dose of RUXOLITINIB to 15 mg BID or 10 mg BID are acceptable in patients who have toxicity but are having benefit from the treatment. If patients develop significant myelosuppression that is thought to be specifically related to RUXOLITINIB, it can be held for a week and then resumed at a lower dose (5-10 mg per day less than the prior dose).

Toxicities to be monitored include any grade 3 or 4 non-hematological toxicity felt to be related to RUXOLITINIB and prolonged cytopenias (lasting for more than 42 days after the initiation of the treatment) felt to be related to the treatment and not the underlying disease. Patients with prolonged cytopenias should have a bone marrow exam around day 42 to establish whether this is due to the treatment or whether there is persistent disease. In the case of the former, treatment should be discontinued.

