## 9.0 EVALUATION DURING TREATMENT/INTERVENTION

### Response assessment

Response assessment (RA) can be performed at the end of any cycle after cycle 1. Specific events that will prompt response assessment include of resolution of splenomegaly on exam and clearance of blasts from the peripheral blood, which will prompt bone marrow aspirate and biopsy. Patients continuing to maintain at least SD by the response criteria shown below should continue to receive ruxolitinib and decitabine until progression of disease, unacceptable toxicity or patient withdrawal. Patients may receive up to 24 cycles in this study. Patients may proceed to allogeneic stem cell transplant at any time after Cycle 1. Dose modification of ruxolitinib will be allowed after Cycle 1. RUXOLITINIB will be provided by the sponsor for a maximum of up to 2 years, after which it will be required to procure it from commercial sources.

Adverse events will be captured as long as patients are on study and will be used to fully characterize the tolerability and toxicity of this combination therapy. These events will be defined based on the NCI CTCAE version 4. Patients who withdraw from the study for any reason will be followed and seen 28 days (+/- 5 days) for an end of study visit to capture all adverse events.

Adverse events will only be captured after the first dose of RUXOLITINIB has been administered.

**Table 3** - Schedule of study procedures

Evaluation	Baseline screening	Cycle 1	Cycle 2 and beyond	Response assessment	End of Study
		At least once weekly (+/- 3 days)	At least once every 2 weeks (+/- 3 days)		(+/- 5 days)
History	x				
physical exam	x	x	x		x
Vital signs	x	x	x		x
Concomitant medications 	x	x	x		x
Adverse event assessment		x	x		x
HIV, HBV, HCV serology	x				
MUGA or Echo	x				
ECG	x				x
CT/MRI abd/pelvis without contrast,	x			x 	

if clinically indicated					
Pregnancy test	X				
CBC with differential	X	X	X		X
Chemistry 	X	X	X		X
Bone marrow biopsy	X			X 	X
Bone marrow aspirate	X			X 	X
Jak2/MPL allele burden 	X				
Correlative studies 	X				X
Chest X-ray	X				

1. Preferentially performed on the marrow, but will be performed on the peripheral blood if a specimen cannot be obtained. Allele burden will not be repeated if neither Jak2 nor MPL is mutated. The sample will be obtained in 5 ml EDTA tube.

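### Cycle 1 ruxolitinib changes fall under conflicting rules, and the plan does not say how a patient held or reduced for a non-DLT event counts towards the MTD

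*Combined protocol and SAP*

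**What the plan says.** **Timing of dose changes.** Sections 3.1 and 8.3 carry the same sentence: "No dose modification will occur until any potential DLTs is fully assessed". Section 3.1 adds: "After the first cycle of therapy, modifications to the dose of Ruxolitinib felt to be in the best interest of the patient are allowed". Section 9.0 says: "Dose modification of ruxolitinib will be allowed after Cycle 1".

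Table 2, also in Section 8.3, sets the criteria for modifying ruxolitinib and is limited to toxicity clearly related to ruxolitinib rather than to the disease. Its action column is headed "At any time during a cycle of therapy (including intended day of dosing". Most rows direct an interruption, and many then a restart at a lower Table 5 level. Only the anemia row carries a cycle limit ("only requires dose reductions after cycle 6").

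Section 8.1, on induction in phase I and II, adds that if significant myelosuppression is thought specific to ruxolitinib, "it can be held for a week and then resumed at a lower dose".

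**Counting.** Section 8.3 states: "DLTs will be defined as those adverse events occurring in the first cycle (i.e. 28 days) of therapy". A hematologic event is a DLT only if it is grade 4, lasts at least 42 days, and comes with marrow cellularity of 5% or less and no leukemia. On replacement, the text under Table 1 says: "Patients who come off the study during the first cycle for reasons other than development of dose limiting toxicity (e.g. disease progression) will be replaced". Sections 8.1, 8.2 and 13.0 refer to evaluable patients, but no section defines the term. Section 13.0 sets the MTD as the highest level with six patients treated and at most one DLT in cycle 1.

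**The concern.** There are two linked problems.

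First, a site facing grade 4 cytopenia attributed to ruxolitinib in cycle 1 has one rule telling it to wait and another telling it to interrupt. Different patients in the same cohort could be handled differently.

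Second, if ruxolitinib is held or reduced for an event that is not a DLT, the patient may receive well under the assigned dose during the DLT window. Nothing removes that patient from the count. Dose escalation presumes that toxicity rises with exposure. On that premise, counting reduced exposure as full exposure lowers the observed DLT rate and can raise the declared MTD. The dose chosen in phase I is then the starting dose for up to 24 phase II patients.

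**Working it through.** **1. Can the timing rules all be followed?** Take a ruxolitinib-attributed ANC below 0.5 × 10⁹/L in cycle 1.
- Table 2 says interrupt, with no waiting period.
- The shared 3.1/8.3 sentence says no modification until a potential DLT has been fully assessed. Whether this event is a DLT depends on a duration of at least 42 days, longer than the 28-day cycle.
- Treating a hold as something other than a modification does not help, because Table 2 lists interruptions under dose modification guidelines.
- Since only the anemia row has a cycle limit, the other rows appear to apply from cycle 1.

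**2. Which held patients are affected?** Only those whose trigger is not a DLT under 8.3. Examples are platelets below 20 × 10⁹/L, grade 4 neutropenia lasting less than 42 days, and grade 2 diarrhea. A hold for an event that meets the DLT definition is already counted.

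**3. How would such a patient count?** The patient stays on study, so the replacement sentence does not apply. No minimum exposure excludes the patient and no DLT has occurred. The default is one DLT-free patient at the assigned level. As a constructed extreme, ruxolitinib held from day 8 with no recovery by day 28 gives 7/28 = 25% of planned dosing days.

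**4. The plan's own figure.** The MTD limit is 1 of 6: 1/6 = 16.7%, stated as 17%. It reproduces. The plan gives no operating characteristics for the 3+3 design, so nothing further can be reproduced.

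**5. Illustration.** All rates here are assumptions; the documents give none. The event is the MTD criterion, at most 1 DLT in 6. Assume a DLT probability of 0.40 at full exposure and 0.10 to 0.20 in a held patient.
- No holds: 0.6⁶ + 6(0.4)(0.6⁵) = 0.0467 + 0.1866 = 0.233.
- One in three held (4 full, 2 held):
  - held risk 0.20: 0.6⁴·0.8² + 4(0.4)(0.6³)·0.8² + 0.6⁴·2(0.2)(0.8) = 0.0829 + 0.2212 + 0.0415 = 0.346
  - held risk 0.10: 0.1050 + 0.2799 + 0.0233 = 0.408
- Two in three held (2 full, 4 held):
  - held risk 0.20: 0.6²·0.8⁴ + 2(0.4)(0.6)·0.8⁴ + 0.6²·4(0.2)(0.8³) = 0.1475 + 0.1966 + 0.1475 = 0.492
  - held risk 0.10: 0.2362 + 0.3149 + 0.1050 = 0.656

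**6. Sensitivity to the assumptions.** Let p be the full-exposure DLT rate, h the share held (independent of DLT risk), and r the fraction of risk a held patient keeps. The counted rate is p(1 − h(1 − r)). P(at most 1 in 6):

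| p | no holds | r = 0; h = 20 / 40 / 60% | r = 0.5; h = 20 / 40 / 60% |
|---|---|---|---|
| 0.30 | 42% | 56 / 70 / 84% | 49 / 56 / 63% |
| 0.40 | 23% | 38 / 56 / 75% | 30 / 38 / 46% |
| 0.50 | 11% | 23 / 42 / 66% | 16 / 23 / 32% |

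The direction is the same throughout. The size ranges from a few points to more than fifty, depending on the assumptions.

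**The case against.** The case on the other side has real force on several points.

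- **A reader might infer that 3.1 and 9.0 ban cycle 1 changes outright.** They do not. Both give permission after cycle 1 without making it exclusive, and the 3.1 wording concerns changes in the patient's best interest. The express bar is the one sentence shared by 3.1 and 8.3, and it is tied to potential DLTs. It need not reach a trigger such as grade 2 diarrhea.
- **Table 2 is narrower than its thresholds suggest.** The toxicity must be clearly related to ruxolitinib. Phase I enrolls relapsed or refractory AML, and myelosuppression is the main anticipated effect of decitabine (Section 10.0), so many low counts may never trigger it. The Section 8.1 hold is optional. Nothing in the documents supports a hold rate of one in three or two in three.
- **Counting held patients as DLT-free is not written anywhere.** It follows from silence plus the replacement sentence. The accurate statement is that their status is undefined.
- **There are safeguards.** A cohort summary goes to the IND Medical Monitor before any dose level change. Phase II toxicity is monitored, and Table 9 gives at least a 93% chance of stopping at a true toxicity rate of 40%.

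These points limit the size of the problem but do not remove it. The conflict remains for ruxolitinib-attributed grade 4 cytopenia. No rule requires dose intensity in the cohort summary or says what to do about it. Phase II stopping acts only after patients have been treated at the chosen dose; Table 9 shows an average of 7 to 8 patients at 40% toxicity.

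**Conclusion.** The concern holds in two parts. The timing rules conflict for ruxolitinib-attributed grade 4 cytopenia in cycle 1; this rests on the text alone. The DLT status of patients held or reduced in cycle 1 for non-DLT events is undefined, and the default reading can bias the DLT rate down and the MTD up. The direction follows if toxicity depends on exposure.

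The size is unknown. The rise from 23% to 35–41% or 49–66% illustrates assumed rates and does not estimate what will happen in this trial. It is also the chance that a level meets the six-patient criterion, not the full probability that it is declared the MTD, which depends on the other levels too.

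A reader might go further and conclude that the MTD will be set too high, or cite the larger figures for clearing a level for escalation (31% with no holds, 71–91% if every patient is held, on the same assumed DLT rates). The documents do not support that: they give no hold rate, and clearing a level is a weaker event than meeting the MTD criterion.

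**What to change.** 1. Reconcile Sections 3.1, 8.3 and 9.0 with Table 2 and the Section 8.1 induction text, so that one statement governs ruxolitinib changes in cycle 1 of phase I. Which rule applies is for the investigators to decide.
2. In Sections 8.2 and 13.0, define a DLT-evaluable patient as one who had a DLT, or who completed the DLT window with at least a prespecified share of planned cycle 1 ruxolitinib at the assigned level.
3. State how held or reduced patients below that share are counted or replaced. The replacement sentence under Table 1 covers only patients who come off study, so it would need extending, within the 6 phase I replacements that Section 6.0 allows.
4. Report cycle 1 dose intensity by dose level in the cohort summary to the IND Medical Monitor.

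**Cost.** Protocol wording, a few replacements, and possibly a lower reported MTD. If replacement is chosen, it can err towards caution, because held patients with a DLT are kept and those without are dropped. With p = 0.40, h = 0.40 and r = 0.5, the counted rate becomes 0.32/(0.60 + 0.40 × 0.20) = 0.32/0.68 = 47%, and P(at most 1 in 6) falls to 14%, against 23% with no holds. The exposure share and the counting rule should be chosen with this in view.
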